Study Population: Recipient subjects will be hospitalized patients aged 18 years or older with severe or life-threatening COVID-19 disease within 21 days or less from beginning of illness. Donor subjects will be people aged 18 years or older who are able to donate blood per standard blood bank guidelines; have prior diagnosis of COVID-19 documented by a laboratory test; and have complete resolution of symptoms at least 28 days prior to donation.

Study Duration: April 1, 2020 to December 31, 2022

Study Design: This a prospective open label pilot study to assess the feasibility of delivering anti-SARS-CoV-2 convalescent plasma to hospitalized patients aged 18 years of age or older, with severe or life-threatening COVID-19 disease less than 21 days from the beginning of their illness. We plan a targeted recruitment of 100 total eligible donor to donate plasma. A total of 10 eligible recipient subjects will receive anti-SARS-CoV-2 plasma after eIND application to the FDA has been approved for each individual subject.

The following will be assessed in all donor subjects

- Biomarker tests performed in the research lab (e.g. antibody titer, cytokine levels)
- Donor questionnaire
- Donors screened as above must be otherwise eligible, give consent, and successfully donate plasma, as part of a whole blood (WB)

The following will be assessed in all recipient subjects:

- Feasibility: is plasma given to the recipient
- All demographic and clinical data contained in the electronic medical record, as well as hospital administrative data for enrolled patients. This data includes age, sex, comorbidities, date of symptom onset, type of admission, APACHE score, SOFA score, clinical status, vital signs including temperature, respiratory rate, oxygen saturation, oxygen requirement, CBC with neutrophil counts, lymphocyte count, complete metabolic panel, liver function tests, CRP, chest x-ray, chest CT, location in hospital.
- Safety and efficacy: Day 0 (baseline), 1, 2, 3, 7, 14, and 28 and once monthly at 2-3 months.

- SARS-CoV-2 PCR from nasopharyngeal swabs: Day 0, 3, 7, 14 to assess viremia response. Other clinically-approved SARS-CoV-2 testing may be used if available (e.g. saliva, nares, blood).
- Biomarker tests performed in the research lab (e.g. antibody titer, cytokine levels) on day 0, 1, 3, 7, 14, additional days 21 and 28 may be included, as available.

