Evaluate the safety of investigational treatment with anti-SARS-CoV-2 plasma in hospitalized patients with severe or life-threatening COVID-19

Secondary Objectives:

Biomarker tests performed in the research lab (e.g. antibody titer, cytokine levels) at days 0, 1, 3, 7 and 14 (additional days 21 and 28 may be included, as available) in the recipient.

Measure rates, levels and duration of SARS-CoV-2 RNA in nasopharyngeal swabs using RT-PCR among recipients. Other specimen types may be tested as available (eg., BAL fluid, tracheal secretions, sputum, etc.) or when RT-PCR assays are validated for additional sources (i.e., stool, blood).

Definitions

- Enrolled: From time consented to participate until designated as a screen failure or have either been discontinued from the study or completed it.
- Screen Failures: signed informed consent, but then determined to be ineligible or withdraws
- Discontinued: withdrawn by investigator or withdraws consent
- Completed: Subjects are considered to have completed when they are followed through day 90 or have had an adverse event or death occurred prior to day 90.

Study population

Plasma Donor Subject Inclusion Criteria for Enrollment

- Age 18 or older
- Able to donate blood per blood bank standard guidelines
- Prior diagnosis of COVID-19 documented by a laboratory test. Patients outside of the UCMC medical system will be asked to provide documentation of COVID-19 positive test.
- Complete resolution of symptoms at least 28 days prior to donation
- Female donors who have never been pregnant, previously pregnant female donors negative for HLA antibodies (HLA screening), or male donors

Plasma Donor Subject Exclusion Criteria for Enrollment

- Unable to give consent
- Unable to donate blood per blood bank standard guidelines
- Unsuccessful blood donation

Plasma Recipient Subject Inclusion Criteria for Enrollment

- Patients must be 18 years of age or older
- Must have laboratory-confirmed COVID-19
- Must have severe or immediately life-threatening COVID-19
 - Severe defined as dyspnea, respiratory frequency \geq 30/min, blood oxygen saturation \leq 93%, partial pressure of arterial oxygen to fraction of inspired oxygen ratio $<$ 300, and/or lung infiltrates $>$ 50% within 24 to 48 hours

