A secure email address at the University of Chicago has been made. . Emails to this address will generate an automatic reply (detailed in the attached recruitment materials). Emails will be viewed by the study staff who will be able to respond if potential participants want to learn more about this research study.

Schedule of Events

Schedule of Events for Plasma Donor Subjects

Table 1. Schedule of events for plasma donor subjects:

| Study period | Screen | Enroll | | Donation |
|--|-----------------|-----------------|--|----------|
| Day | -90 to -28 days | -1 days or more | | 0 |
| Test positive for COVID-19 Patients outside of the UCMC medical system will be asked to provide documentation of COVID-19 positive test | x | | | |
| Subject recruitment and screening | | x | | |
| Consent for participation in donor portion of study | | X | | |
| Donor intake questionnaire via redcap. | | X | | |
| Consent for blood donation using standard UCM Blood Donation processes and procedure | | | | x |
| Donation at UCMC Blood Bank | | | | x |

Table 2: Schedule of Events for Plasma Recipient Subject

| Study period | Screen | Baseline | Transfusion | Follow-up | | | | |
|---|---------|----------|-------------------|-----------|---|---|----|-----------------|
| Day | -7 to 0 | 0 | 0 | 1 | 3 | 7 | 14 | 28 ¹ |
| Eligibility | | | | | | | | |
| Informed consent | x | | | | | | | |
| Demographic and Medical history | x | | | | | | | |
| COVID-19 symptom screen | x | | | | | | | |
| Pregnancy test | x | | | | | | | |
| ABO | x | | | | | | | |
| Application for single patient eIND | x | | | | | | | |
| FDA compassionate use for convalescent plasma | | | | | | | | |
| eIND is approved | x | | | | | | | |
| Study Plasma Administration | | | | | | | | |
| Plasma infusion | | | x | | | | | |
| Study Procedures | | | | | | | | |
| Vital signs | x | x | xxxx ² | x | x | x | x | |
| Physical examination | x | | x | x | | x | | |
| Symptom screen | x | x | x | x | x | x | x | x |
| Concomitant medications | x | x | x | | | | | |
| Assessment with 7-point ordinal scale | | x | | x | x | x | x | x |
| Adverse event monitoring | | x | x | x | x | x | x | x |
| Laboratory testing | | | | | | | | |
| CBC and CMP | | x | | x | x | x | x | |
| Chest x-ray or CT chest if available | x | | | x | x | x | x | |
| SARS-CoV-2 RT-PCR | | x | | x | x | x | x | |
| Blood samples for biomarker tests performed in the research lab | | x | | x | x | x | x | |

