Biomarker tests performed in the research lab include antibody titer, neutralizing antibody, cytokine levels, viremia

¹ The assessments performed on day 28 will be repeated on days 60 and 90.

² Vital sign testing: Immediately prior to infusion, 10-20 minutes after start of infusion, at completion of infusion and 30-60 minutes after the end of the infusion

Subject Withdrawal

- Subjects can terminate study participation and/or withdraw consent at any time without prejudice.
- Subjects who withdraw from the study will not be replaced.
- The investigator may withdraw subjects if they are lost to follow up, non-compliant with study procedures or if the investigator determines that continued participation in the study would be harmful to the subject or the integrity of the study data.
- Discontinuation of the study: The IRB has the right to terminate this study at any time

Investigational plasmaTreatment

- Recipient subjects will receive anti-SARS-CoV-2 convalescent plasma as a pilot study after approval of single patient eIND application.
- Recipient subjects will receive anti-SARS-CoV-2 convalescent plasma under IRB20-0825
- Investigational Product: The investigational product is anti-SARS-CoV-2 convalescent plasma obtained from donors identified as having recovered from COVID-19.
- Donors samples will have been screened for transfusion-transmitted infections (e.g. HIV, HBV, HCV, WNV, HTLV-I/II, *T.cruzi*, syphilis, ZIKV) both through the use of the UCM Blood Donation Center Blood Donation Record and FDA-mandated blood donor screening tests. Plasma will have been collected as whole blood derived units donations and in accordance with standard FDA and blood bank protocols. Plasma will be ABO-compatible and HLA-screened per standard FDA and blood bank protocols.
- Recipient subjects will receive 1 unit of convalescent plasma after eIND approval. When CLIA clinical testing for antibody is available, plasma will be transfused with an anti-SARS-CoV-2 titer of >1:320, though this titer may be adjusted as *in vitro* titer assays of virus neutralization are correlated with *in vivo* assessments of virus neutralization.
- Plasma will be labeled according to FDA and blood bank guidelines.

Research biomarkers and other studies

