Unanticipated Problem (UP)

Unanticipated problems involving risks to subjects or others refer to a problem, event or information item that is not expected, given the nature of the research procedures and the subject population being studied; and which suggests that the research places subjects or others at a greater risk of harm or discomfort related to the research than was previously known. The IRB considers unanticipated problems, in general, to include any incident, experience, or outcome that meets ALL of the following criteria:

1. unexpected (in terms of nature, severity, or frequency) given (a) the research procedures that are described in the protocol-related documents, such as the IRB-approved research protocol, investigator's brochure, drug or device product information, informed consent document, or other research materials; and (b) the characteristics of the subject population being studied, including underlying diseases, behaviors, or traits;
2. related or possibly related to participation in the research (possibly related means there is a reasonable possibility that the incident, experience, or outcome may have been caused by the procedures involved in the research); and

3. suggests that the research places subjects or others at a risk of unknown harm or addition/increased frequency of harms (including physical, psychological, economic, legal, or social harm) than was previously known or recognized.

Unanticipated problems may be adverse events, protocol deviations, noncompliance or other types of problems, but MUST meet all of the criteria listed above. It is the expectation of the IRB that all approved protocol procedures are being followed without alteration unless the IRB has been informed of a protocol change or deviation.

Protocol Deviation: Deviation from the IRB-approved study procedures. Designated serious and non-serious

1. **Serious Protocol Deviation:** Protocol deviation that is also an SAE and/or compromises the safety, welfare or rights of subjects or others
2. **Safety Reporting Requirements**

Reporting Interval

All AEs and SAEs will be documented from the first administration of study product until completion or un-enrollment from the study. All AEs and SAEs will be followed until resolution even if this extends beyond the study-reporting period. Resolution of an adverse event is defined as the return to pre-treatment status or stabilization of the condition with the expectation that it will remain chronic.

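### Any adverse event before day 90 makes a recipient 'completed', and AE recording stops at completion; this conflicts with AE follow-up of all recipients to Day 90

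*Combined protocol and SAP*

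**What the plan says.** All references are to the combined protocol and SAP.

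- **Definitions (Investigational plan).** A subject is "completed when they are followed through day 90 or have had an adverse event or death occurred prior to day 90". Enrolled status runs "From time consented to participate until designated as a screen failure or have either been discontinued from the study or completed it". The remaining exit is "Discontinued: withdrawn by investigator or withdraws consent".
- **Reporting Interval (Safety measures).** "All AEs and SAEs will be documented from the first administration of study product until completion or un-enrollment from the study". The next sentence adds: "All AEs and SAEs will be followed until resolution even if this extends beyond the study-reporting period". A further sentence has the investigator report SAEs suspected to be product-related that come to light after study completion.
- **Follow-up schedule.** The Protocol Summary lists, for all recipients, "Safety and efficacy: Day 0 (baseline), 1, 2, 3, 7, 14, and 28 and once monthly at 2-3 months". In Table 2 the row "Adverse event monitoring" is marked at baseline, transfusion and Days 1, 3, 7, 14 and 28, and footnote 1 states: "The assessments performed on day 28 will be repeated on days 60 and 90". The recipient study procedures list AE evaluation at Day 28 and again at Days 60 and 90. Safety measures lists symptom screens on those same days. None of these places excepts a recipient who has already had an AE.
- **Analysis of AE data.** Two proportions are to be reported: subjects with an SAE, and subjects with a Grade 3 or higher AE. Neither is restricted to related events. The Statistical Analysis paragraph sets the default denominator at 10.

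**The concern.** The definition and the reporting interval work as a chain: a first AE means completed, and completed means that AE documentation ends. The trigger is low. The protocol defines an AE as any untoward occurrence, related or not, including an abnormal laboratory finding, and a laboratory rise of 2 s.d. above baseline is itself reportable as an AE. Recipients have severe or life-threatening COVID-19, with blood tests listed for Days 0-7 and 14, so an early first AE is plausible, although the documents give no rate.

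The two AE proportions are at stake. If the definition is applied, a recipient with a minor laboratory AE on Day 1 and a new, non-serious Grade 3 event on Day 10 could be counted as having no Grade 3 event. If the schedule is applied, the same recipient is counted. The text supports both, and the published proportion would not reveal which was used.

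**Working it through.** There is no planned figure to reproduce: the analysis is descriptive, and the documents state no AE rate. The check is a comparison of rules, followed by simple counts.

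**1. The rules for new events after a first AE**

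| Rule | New events recorded after a first AE? |
|---|---|
| Definitions with Reporting Interval, read literally | No |
| Protocol Summary, Table 2 with footnote 1, recipient procedures | Yes, to Day 90 |

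No section gives one precedence over the other.

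**2. How much scheduled follow-up is in dispute**

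The protocol gives the post-infusion assessment days in three ways:
- A, Table 2 with footnote 1: 1, 3, 7, 14, 28, 60, 90 (7 days).
- B, Protocol Summary, with the monthly visits at 2-3 months taken as Days 60 and 90: A plus Day 2 (8 days).
- C, recipient procedures with the Day 1-7 block read as daily, and Day 14 taken from Table 2: 1 to 7, 14, 28, 60, 90 (11 days).

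For a first AE on day d, the assessments outside the literal window are those later than d, and the calendar days outside it are 90 − d.

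| First AE on day | A (of 7) | B (of 8) | C (of 11) | Days outside (of 90) |
|---|---|---|---|---|
| 1 | 6 | 7 | 10 | 89 |
| 3 | 5 | 5 | 8 | 87 |
| 7 | 4 | 4 | 4 | 83 |
| 14 | 3 | 3 | 3 | 76 |
| 28 | 2 | 2 | 2 | 62 |

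These counts show how far the two rules diverge. They are not counts of missed events.

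**3. Effect on a reported proportion**

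If k recipients have their only qualifying event outside the window and unrecorded, the proportion falls by k/10. The value of k is an assumption: k = 0, 1, 2 or 3 gives 0, 10.0, 20.0 or 30.0 percentage points. If the schedule is followed, k = 0.

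**4. What other provisions would recover**

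- Events already recorded are followed to resolution. This does not cover new events.
- Later SAEs suspected to be related are reported if the investigator learns of them. SAEs in general are forwarded to the Independent Safety Monitor and the IRB.
- The protocol team reviews AEs in real time and the Independent Safety Monitor reviews SAEs. Both act only on events that have been captured.
- Source Documents has the database filled from study visits and medical records, and requires those records to show AEs during the trial.
- Death, cardio-circulatory arrest, ICU transfer, respiratory support, vasopressors, renal support and hospital length of stay are collected as outcomes in their own right.

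What remains is mainly a new, non-serious Grade 3 event after a first AE that staff, applying the definition, do not enter as an AE.

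**The case against.** The best defence is that the literal reading defeats itself. The Medical history item in the recipient procedures treats any condition arising after consent as an AE, so a recipient could be completed before plasma was given. A routine laboratory rise could complete a very ill inpatient on Day 1. That would empty the Day 28, 60 and 90 AE evaluations of purpose, together with the quarterly aggregate AE review and the halting criterion that looks for a pattern of individually minor events. The Definitions section is a list of status labels, and every operational section on follow-up points to Day 90. Source Documents also gives a route into the database through visits and medical records. Grade 3 here means escalation of treatment, so many such events would leave a trace in the respiratory, vasopressor, renal or length-of-stay outcomes.

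Most of this stands. It makes a drafting slip the likely explanation and leaves a small residual risk. It does not remove the conflict: the Reporting Interval uses completion as its stopping point, so the label has an operational effect. A trace in another outcome is also not an AE record, and the proportions count AEs.

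A reader might infer that recipients leave follow-up after a first AE, or that the SAE proportion will be understated. The documents support neither. The visit schedule has no such exit, and the SAE provisions above would recover many serious events. Nor do they show that the halting criteria fail: those criteria are not tied to the reporting interval, and the laboratory tests are scheduled for every recipient through Day 14.

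**Conclusion.** The text is wrong as written, and the consequence is minor. The conflict is certain from the wording. Any loss of data depends on staff applying the definition instead of the schedule, which the documents neither require clearly nor rule out.

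If they did apply it, the bias would be downward, chiefly in the Grade 3 or higher proportion, by 10.0 percentage points for each recipient whose only qualifying event was missed. How many that would be cannot be derived from the documents, and it is zero if the schedule is followed. The first primary safety endpoint, rapid deterioration during transfusion, is essentially untouched. The product-related events named in the second would be reported if serious and known to the investigator. What is left even in the favourable case is that a reader of the results could not tell which AE window lies behind the two proportions.

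**What to change.** 1. In Definitions, remove the adverse-event route to completion: *Completed: followed through day 90, or death before day 90.*
2. In Reporting Interval, replace the end point: *AEs and SAEs are documented through day 90, death or discontinuation, whichever is first.* Discontinuation already means withdrawal of consent or withdrawal by the investigator, and Subject Withdrawal lists loss to follow-up among the investigator's grounds.
3. Keep the follow-to-resolution sentence and the sentence on related SAEs after completion.
4. Reconcile the start of the window. Reporting Interval begins at first administration, whereas the Medical history item treats conditions arising after consent as AEs. State one start and use it in both places.
5. Give the AE window with the two proportions when they are reported.

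The cost is a few words of protocol text and, at most, slightly more AE recording at visits already scheduled. No visit, test or subject is added.

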Finally, there are risks associated with any transfusion of plasma including transmission of transfusion transmitted viruses (e.g. HIV, HBV, HCV, etc.), allergic transfusion reactions, anaphylaxis to transfusion, febrile transfusion reaction, transfusion related acute lung injury (TRALI), and transfusion associated cardiac overload (TACO). Infectious risks are minimized by collecting only eligible donors and testing donors for all FDA-required infectious diseases as part of standard allogeneic donor blood collection. TRALI is mitigated by collecting male donors, female donors who have never been pregnant, or previously pregnant women who are negative for HLA antibodies. Donors will fulfill all donor requirements for whole blood donation. The standard volume of plasma (~300 mL) will be transfused over a longer time period (4 hours) and the patient will be monitored for signs of overload.

Known potential benefits

A key potential benefit is the potential treatment for established infection. Convalescent plasma would be administered to those with clinical disease in an effort to reduce their symptoms and mortality. Based on the recent evidence from China with antibody administration, it can be anticipated that *antibody administration in patients with severe COVID-19 could improve mortality, decrease ICU needs and reverse ventilator- or oxygen-dependence in carefully selected patients.*

Given that historical and current anecdotal data on use of convalescent plasma suggest it is safe in coronavirus infection, the high mortality of COVID-19, particularly in elderly and vulnerable persons, suggests that the benefits of its use in those at high risk for disease outweigh the risks. However, for all cases where convalescent plasma administration is considered, a risk-benefit assessment must be conducted to assess individual variables.

Investigational plan

Study Objectives

Primary Objective:

1. Feasibility of performing clinical pathway for convalescent plasma therapy consisting of consenting convalescent donors, harvesting anti-SARS-CoV-2 convalescent plasma, application for single patient eIND to the FDA and administering anti-SARS-CoV-2 convalescent plasma to the patients meeting study criteria
2. Type and duration of respiratory support (e.g. CPAP, BiPAP, high-flow nasal cannula, mechanical ventilation)

Primary Safety Objective:

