During standard whole blood donation, peripheral blood mononuclear cells (PBMCs) are collected by the leukoreduction filter. This filter is normally discarded. Instead of discarding this filter as per usual practice, the filter will be labeled with the donor identification number and will be given to [name]'s laboratory for the isolation of B cells reactive to recombinant proteins from SARS-CoV-2 for the synthesis of monoclonal antibodies. These antibody proteins will be characterized for binding to COVID-19 proteins and other protective activities against the virus. These antibodies will be valuable as possible therapeutic agents or for the production of high-sensitivity

and high-specificity diagnostic reagents. These antibodies will also guide and template the generation of vaccines to protect against COVID-19. A small aliquot of serum from the patient blood samples will also be analyzed for binding to the various COVID-19 proteins we have access to by ELISA to learn which COVID-19 proteins are the most immunogenic, further guiding vaccine design efforts.

Per FDA guidelines, convalescent serum containing neutralizing antibody with a titer optimally greater than 1:320 should be used when antibody titer tests are available. Antibody testing is currently only available in research labs ([name] at the University of Chicago). When antibody testing is available in clinical labs, we will be able to use titer information to guide plasma transfusion, e.g. titer can be adjusted as *in vitro* titer assays of virus neutralization are correlated with *in vivo* assessments of virus neutralization. This will identify individuals who have anti-SARS-CoV-2 neutralizing antibody and identify the strength of the virus-neutralizing antibody in each titer concentration.

Rationale for doses

The dose of 1 unit; ~300 mL was chosen to minimize volume given to a patient with compromised pulmonary function/acute respiratory distress syndrome, which fits the profile of COVID-19 patients with severe disease.

Investigational treatment-plasma administration

- Plasma will be administered after enrollment and approval of single patient eIND by the FDA or under the expanded access protocol IRB20-0825
- Infusion rate will be ~300 mL over 4 hours (~50 mL per hour)
- Pretreatment to minimize transfusion reactions (e.g. acetaminophen, diphenhydramine) may be given per investigator and clinical care team discretion.

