- If an AE develops during infusion, the infusion may be slowed or stopped as per investigator's decision.
 - Most reactions to plasma are relatively minor and the infusion can generally be continued. Infusion site burning and non-allergic systemic effects can generally be managed with slowing of the infusion. Infusion can generally be continued in cases of itching or hives after pausing the transfusion, administering antihistamines, and observing the patient for worsening.
 - Severe allergic reactions such as, bronchospasm and hypotension, and may require discontinuation of the infusion.

Concomitant medications will be documented on the CRF

- Prescription medications
- Over the counter medications

- Herbal treatments/nutritional supplements
- Blood products

Statistical considerations

Statistical Analysis

This is a pilot study focused on determining the protocol feasibility with limited subject enrollment. Therefore, statistical analysis will include descriptive summaries of both the primary and secondary outcomes of interest. For continuous variables we will determine: median, minimum and maximum values. Categorical variables will be summarized by the frequency. Unless otherwise indicated, percentages in tables will be column percentages, using the total number of observations in the population ($n=10$), as the denominator. Percentages will be rounded to one decimal place, and thus may not always add up to exactly 100%. Clinical laboratory values will be first reported in using International System of Units (SI).

Analysis of AE data

Analysis of AE data will primarily be descriptive based on MedDRA coding of events. The proportion of subjects experiencing an SAE and the proportion experiencing a Grade 3 or higher AE will be measured.

Analysis of SARS-CoV-2 viremia

Analysis of SARS-CoV-2 viremia will primarily be descriptive, comparing the viremia levels at days 0,1,3,7 and 14 between the subject recipients.

Analysis of research biomarkers

Analysis of biomarker tests performed in the research lab such as antibody titers, cytokine levels will primarily be descriptive, comparing the titers at days 0,1,3,7 and 14 between subject recipients.

Endpoints

Primary Endpoint:

1. Feasibility of performing study pathway consisting of consenting convalescent donors, harvesting convalescent plasma, application for FDA eIND and administering convalescent plasma to the patients

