 - Medical history (timing of exposure to COVID-19 source patient, acute and chronic medical condition, medications, allergies, any drug trial therapy. Any medical condition arising after consent should be recorded as AE)
 - COVID-19 symptom screen (fevers, cough, shortness of breath), day of onset of symptoms
 - Vital signs
 - COVID-19 testing (RT-PCR) from nasopharyngeal, throat, blood or stool (optional) samples. Other clinically-approved SARS-CoV-2 testing may be used if available (e.g. saliva, nares, blood).
 - Blood typing, CBC, comprehensive metabolic panel
 - Urine or serum pregnancy test for females of childbearing potential. Results from laboratory tests obtained up to 7 days before enrollment may be used for the pregnancy test.
 - Stored samples for biomarker tests performed in the research lab (e.g. antibody titer, cytokines)
 - Determination of eligibility as per inclusion/exclusion criteria
4. Application and approval of eIND per FDA guidelines for single patient compassionate use of convalescent plasma

DAY 0:

1. Study Plasma Administration: 1 unit of plasma will be transfused. Time at start and end of infusion will be recorded and Vital signs will be measured immediately prior to infusion, 10-20 minutes after start of infusion, at completion of infusion and 30-60 minutes after the end of the infusion
2. COVID-19 symptom screen (fevers, cough, shortness of breath)
3. Assessment of clinical status (7-point ordinal scale)
4. New medical conditions, concomitant medication, AE evaluation
5. physical examination
6. Blood typing, CBC, comprehensive metabolic panel, C-reactive protein
7. Stored samples for biomarker tests performed in the research lab (e.g. antibody titer, cytokines)

Day 1-7 (or for duration of hospitalization)

1. Vital signs daily
2. COVID-19 symptom screen (fevers, cough, shortness of breath)
3. Assessment of clinical status (7-point ordinal scale)
4. New medical conditions, AE evaluation
5. physical examination
6. CBC, comprehensive metabolic panel, CRP daily
7. COVID-19 testing (RT-PCR) from nasopharyngeal, throat, blood or stool (optional) samples. Other clinically-approved SARS-CoV-2 testing may be used if available (e.g. saliva, nares, blood)

8. Stored samples for biomarker tests performed in the research lab (e.g. antibody titer, cytokines)

Day 28:

Key issues to consider follow up by phone, alive, at home, in hospital (ICU or not), on supplemental O2 or not, back to work, fully, partially, SNF, nursing home, LTAC

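### The infusion rate is misstated: about 300 mL over 4 hours is about 75 mL per hour, not 50; separately, two instructions on isolated hives or itching conflict when read literally

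*Combined protocol and SAP*

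**What the plan says.** **Rate.** The only line that sets a rate is in *Investigational treatment-plasma administration*: "Infusion rate will be ~300 mL over 4 hours (~50 mL per hour". *Known potential risks* gives the same volume and time without a rate: "The standard volume of plasma (~300 mL) will be transfused over a longer time period (4 hours". It adds that "the patient will be monitored for signs of overload". *Study Agent* in the protocol summary and *Rationale for doses* both put one unit at about 300 mL. According to the latter, the dose "was chosen to minimize volume given to a patient with compromised pulmonary function/acute respiratory distress syndrome". The Day 0 procedures for recipients say that "1 unit of plasma will be transfused" and require the start and end times to be recorded. Vital signs are taken just before the infusion and then "10-20 minutes after start of infusion, at completion of infusion and 30-60 minutes after the end of the infusion".

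**Skin reactions.** The administration section says: "If an AE develops during infusion, the infusion may be slowed or stopped", at the investigator's decision. It continues: "Infusion can generally be continued in cases of itching or hives after pausing the transfusion", with antihistamines and observation for worsening. *Halting Criteria/Rules for Subject Infusion* takes a different line. It lists manifestations of anaphylaxis, any one of which stops the infusion with no restart, and hives and pruritus are on that list.

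**The concern.** A pump is set in mL per hour, and the one line that supplies this setting contradicts itself. Staff who follow the bracketed rate run about 6 hours; staff who follow the duration run 4. The recipients have compromised lungs, and the plan presents both the small volume and the slow delivery as precautions, so the instruction should be unambiguous.

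The skin-reaction texts raise a similar problem of consistency. The same isolated hives could lead one clinician to pause and resume and another to stop permanently, each with support in the protocol.

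**Working it through.** **Inputs.** Volume V = about 300 mL (*Study Agent*, *Known potential risks*, *Rationale for doses*, administration section). Duration T = 4 h (*Known potential risks*, administration section). Stated rate R = about 50 mL/h (administration section only).

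**Attempt to reproduce the plan's rate.** R = V / T = 300 / 4 = 75 mL/h. The stated 50 mL/h is not reproduced. Shortfall: (75 − 50) / 75 = 33%.

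**Which input would have to change for 50 mL/h to be right?**
- Holding 4 h: V = 50 × 4 = 200 mL, which is 100 mL short of the stated unit.
- Holding 300 mL: T = 300 / 50 = 6 h.

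**Can the approximation signs absorb the gap?** The documents give no range for unit volume, so the values below are assumed for illustration, with T = 4 h.

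| Assumed volume (mL) | Rate over 4 h (mL/h) | Time at 50 mL/h (h) |
|---|---|---|
| 200 | 50.0 | 4 |
| 250 | 62.5 | 5 |
| 300 | 75.0 | 6 |
| 350 | 87.5 | 7 |

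Only a 200 mL unit fits, a third below the stated average. Stretching 300 mL over 5 h still gives 60 mL/h. Rounding does not explain the discrepancy.

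**Effect on scheduled vital signs.** The interval from the check at 10–20 minutes to the check at completion is:
- at 75 mL/h: 240 min minus 10 to 20 = 220 to 230 min;
- at 50 mL/h: 360 min minus 10 to 20 = 340 to 350 min.

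The checks are tied to events, so they are defined at either rate. Most of the long interval comes from the schedule; the slower rate adds 120 minutes.

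**Skin reactions, texts side by side.**

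| Isolated itching or hives | Administration section | Subject halting rule, read literally |
|---|---|---|
| First step | Pause, antihistamines, observe | Halt |
| Resume? | Generally yes | No |

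The halting rule introduces its list as manifestations of anaphylaxis, so it can also be read as not reaching an isolated skin sign. Two things support that reading: the administration section has a separate tier for severe allergic reactions, and criterion 2 for halting the whole study describes life-threatening anaphylaxis in terms of bronchospasm. On the other side, the rule says any listed sign suffices, its last item allows a halt before full SAE criteria are met, and it does not refer back to the administration section.

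**The case against.** The best defence on the rate is that little turns on it. Volume and duration are repeated elsewhere, so a careful reader can see that the bracketed figure is the odd one out. Either rate delivers the full unit if the infusion runs to completion. Actual start and end times are recorded for each of the ten planned recipients. This stands, and it is why the point is minor. It does not remove the error, because the faulty figure sits in the operative instruction.

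A reader might infer a risk of circulatory overload. The documents do not support that: the wrong figure is the slower one, and overload monitoring is planned. Nor does the vital-signs interval make this a safety failing. It is already 220 to 230 minutes at the correct rate, and Table 2 also marks symptom screening and adverse event monitoring at transfusion.

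On skin reactions, a reader might conclude that the protocol is silent on hives. It is not: both sections address them, and the difficulty is that they differ. It is fair to reply that clinical judgement, together with the narrower reading of the halting rule, may reconcile the two. That reading is available but not written down. It is also a fair objection that confining permanent halting to full anaphylaxis, or to skin signs with respiratory or haemodynamic involvement, could loosen the rule for isolated tongue or uvula swelling or isolated hypotension. That objection stands, and the fix below avoids it.

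**Conclusion.** The rate error is certain as arithmetic: the stated 50 mL per hour is one third below what the stated volume and time imply. That 75 mL per hour was intended is probable, since both 300 mL and 4 hours recur elsewhere and 50 appears once, but the documents do not prove it. The consequence is confined to how long the infusion runs, or how much has been given by 4 hours.

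It would be too strong to say that the rate error threatens the feasibility result. That criterion asks for six or seven of ten recipients to complete the infusion with at least 24 hours of follow-up data, and a 4-hour or a 6-hour infusion can meet it. The sample size and the descriptive analysis do not depend on the rate.

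The skin-reaction point is secondary and less certain: a conflict on the literal reading, an ambiguity on the narrower one. Which instruction prevails could decide whether a given subject completes the infusion. The documents give no frequency for such reactions, so no effect on the feasibility count can be sized and none is claimed.

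**What to change.** In *Investigational treatment-plasma administration*, change the bracketed rate to about 75 mL per hour, which agrees with *Known potential risks*. If the sponsor meant 50 mL per hour, change the duration to about 6 hours in both sections instead.

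Separately, add one sentence stating whether the administration section or the subject halting rule governs isolated hives or itching. That is the sponsor's clinical decision, and either answer resolves the conflict. Confine the sentence to those two signs and leave every other halting trigger unchanged, including swelling of the lips, tongue or uvula, respiratory compromise, a fall in blood pressure and heart-rate changes.

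The cost is a short amendment: one figure (or one duration in two places) and one sentence, with no added procedures or patients.
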